## **I. BACKGROUND AND SIGNIFICANCE:**

Rhabdomyosarcomas account for 3.8% of solid malignancies in children under the age of 19 years. There are 320 cases per year in the United States[1]. It is a curable disease in most children with localized disease who receive combined modality therapy, with more than 70% surviving 5 years after diagnosis[2-4]. The most common primary sites for rhabdomyosarcoma are the head and neck (e.g., parameningeal, orbit, pharyngeal, etc.), the genitourinary tract, and the extremities[2,4] Other less common primary sites include the trunk, chest wall, the abdomen (including the retroperitoneum and biliary tract), and the perineal/anal region. Most cases of rhabdomyosarcoma occur sporadically with no recognized predisposing factor or risk factor[5], although a small proportion are associated with genetic conditions.

In the 1970's, a combined modality approach of radiation, chemotherapy and surgery when possible for rhabdomyosarcoma (RMS) was introduced and refined over the past three decades by the Intergroup Rhabdomyosarcoma Study (IRS) group who are on their fifth generation of trials IRS V (protocol D9803, D9602, D9501).

The prognosis for a child or adolescent with rhabdomyosarcoma is related to the site of origin, resectability, presence of metastases, number of metastatic sites, and histopathology[4-7]. Embryonal histology is more favorable than alveolar or undifferentiated. Certain areas are considered favorable sites such as the orbit, non-parameningeal head and neck, non-bladder/prostate GU. All other sites such as trunk, parameningeal, bladder/prostate and extremity are considered unfavorable.

Pediatric patients with RMS are categorized by stage and group. Staging helps determine what risk category patients are in and grouping helps determine the need and dose for radiation therapy.

### **Grouping: The IRS Grouping System (5 yr OS from IRS III)**

Group I: Localized disease, completely resected (93%)

- a. Confined to muscle or organ of origin
- b. Infiltration outside the muscle or organ of origin

Group II: Total Gross Resection with: (81%)

- a. Microscopic residual disease
- b. Regional lymphatic spread, resected
- c. Both

Group III: Incomplete Resection with Gross Residual Disease (73%)

- a. After Bx only
- b. After major resection (>50%)

Group IV: Distant metastatic disease present at onset. (30%) (If bone metastases are present at diagnosis, then there is only 10% chance of cure.[8])

### TNM Pretreatment Staging Classification:

Stage	Sites	T (confined?)	T size	N	M	5 yr OS
I	Orbit, H and N, GU-non bladder/prostate	Either	A or B	Any	0	89%
II	Bladder/Prostate, Extremity, Parameningeal, (Other, trunk, retroperitoneal)	Either	A ( $\leq$ 5 cm)	N0, Nx	0	86%
III	Same as II but either large or node +.	Either	A B	N1 N0-1	0	69%
IV	All				1	30%

T1: confined to anatomic site of origin, T2: extension beyond anatomic site

A:  $\leq$ 5 cm, B> 5cm

Most of the pediatric patients treated in the United States are treated in major academic centers that participate in the IRS protocols. Chemotherapy and radiation therapy is dictated by the protocol upon which the patient is treated (currently IRS V). If a patient is not on-protocol already they will be treated according to the guidelines of either IRS IV or IRS V. IRS IV was the last completed trial that showed further gains in tumor control compared with previous trials (IRS I-III). The use of radiation therapy to attain the highest rates of local control for patients with microscopic residual disease, gross unresectable disease, or fully resected tumors with alveolar histology is now the standard of care in the United States and based upon these IRS I-IV studies.

However, radiation therapy in the pediatric population can be associated with long-term and short-term morbidity, depending upon the volume treated and the dose delivered. In order to sterilize a tumor with radiation, normal tissues invariably are treated in the process. The normal tissue irradiated in the process of treating tumor directly causes morbidity. Organs and tissue growth and development are impaired with increasing doses of radiation. The younger a patient is at the time of treatment the greater the clinical effect of the developmental impairment[9-11].

Acute toxicity and long-term complications from radiation therapy depend on the site being treated, since sarcomas may occur at almost any site in the body. In general, most sarcomas treated with radiation require doses, which may cause acute toxicity necessitating treatment breaks, aggressive symptom management or long-term complications that require medical management as well.

Since the advent of the CT scanner and magnetic resonance (MR) imaging techniques, radiation oncologists have been able to more exactly target tumor within a body by better visualizing it. Furthermore, the CT scanner has become an integral part of treatment planning in radiation therapy. Currently the standard of care widely available in the United States is 3-D CT planned conformal radiation therapy. A further step has been taken to improve the dose to the tumor but reduce dose to surrounding structures called

intensity modulated radiation therapy (IMRT), where blocks are moved in and out of a field in order to better shape the dose distribution around the tumor. IMRT is available in a limited number of centers around the country.

However, both 3-D conformal therapy and IMRT still entail both an entrance dose to normal tissue as it penetrates to reach a tumor at depth in tissue, and an exit dose as it exits the body in a straight path beyond the tumor. Typically, multiple fields are used coming in at different angles all converging on the tumor to spread out the dose to normal tissue, while bringing the tumor to higher, curative doses.

Proton radiation differs from standard radiation (photons) in that the radiation can be stopped at a defined depth in tissue. Therefore, there is no exit radiation dose, sparing all the normal tissues beyond the tumor. Using proton irradiation, more normal tissue can be spared irradiation, resulting in less short-term and long-term morbidity.

Protons have a similar biologic effect to photons against tumors. Their clinical advantage over standard radiation results from the more favorable dose distributions achievable with their particular physical properties. The rapid increase in energy loss at the end of the range of protons results in a rapid increase in dose absorbed and is known as the Bragg peak. By modulating the beam, this Bragg peak can be spread out over the entire target volume to produce a nearly uniform dose distribution. The other advantage of protons is the lack of exit dose beyond the Bragg peak. The accuracy of delivering proton therapy is further enhanced by advancements in treatment planning and delivery technology. The advantage of protons has been demonstrated for medulloblastoma, and comparative treatment planning using protons versus photons have shown a clear advantage to protons in terms of dose distribution [12-20]

The acute toxicity seen with radiation therapy depends on the location of the tumor and the area and volume of tissue necessitating treatment. If a large portion of the vertebral spine or pelvis is being treated, or if combined with chemotherapy, bone marrow suppression can occur. Fatigue and general malaise can occur from treatment involving any part of the body but is usually worse with increasing dose. Treatment to the head and neck area can cause alopecia, dermatitis, folliculitis, irritative conjunctivitis, otitis externa, otitis media, laryngitis and pharyngitis. Acute toxicities from radiation to the thorax include esophagitis, dysphagia, heartburn, pneumonitis, or pericarditis. Radiation to the abdomen and pelvis can cause anorexia, weight loss, nausea, vomiting, gastritis, enteritis, cystitis, nephritis, and /or hepatitis. Any neurologic symptoms produced by the tumor can worsen acutely with treatment but this is usually temporary. Acute symptoms from radiotherapy to tumors in the extremities are usually limited to skin reactions. Acute symptoms may be worse when concurrent chemotherapy is administered.

Long-term complications can start to manifest after about 3 months following completion of radiation therapy and are also specific to the normal tissues irradiated in the process of treating the tumor. Tissues such as muscle, bone, and organs irradiated in a growing child often fail to develop normally which can result in asymmetries and significant cosmetic and/or functional abnormalities.

Complications for cranial irradiation include permanent hair loss, the increased risk of radiation-induced secondary malignancy, neuro-endocrine dysfunction, neurocognitive dysfunction, brain necrosis, neuronal atrophy, persistent edema and vascular abnormalities. Late complications from irradiation in the head and neck region may include: permanent dry mouth or dry eye, cataract formation, retinopathy, chronic otitis media, permanent dysphagia and facial asymmetry. Complications from irradiation to the chest/abdomen or pelvis can result in stunting of growth, asymmetric growth (scoliosis, kyphosis) or restrictive air movement from lung irradiation, primary hypothyroidism, cardiac disease, pneumonitis, peptic ulcer disease, permanent enteritis, gonadal failure or decreased bone marrow reserve.

The proposed treatment regimen of replacing fractionated photon therapy with fractionated proton therapy takes advantage of the superior dose distribution of protons. It is expected that the therapeutic gain will be the greatest in children whose development and tissue maturation can be significantly retarded by the effects of radiation. The risk of induction of second malignancies due to radiation should also be reduced as a result of less normal tissue irradiated.

Patients enrolled on this protocol are often already enrolled on other national pediatric sarcoma protocols such as those testing chemotherapy regimens but also requiring radiation as part of the treatment regimen. Children's Oncology Group (COG) is the body overseeing the IRS studies and has agreed to allow the substitution of proton radiation for photon radiation in the rhabdomyosarcoma protocols. The same radiation treatment parameters such as dose, fraction size, and scheduling will be used as specified in the national protocol in which the patient is participating.

## **II. SPECIFIC AIMS (RESEARCH OBJECTIVES)**

1. To assess late complications from irradiation using proton beam therapy in place of conventional photon beam therapy in pediatric patients with rhabdomyosarcomas.
2. To assess acute side effects from irradiation using proton beam therapy in place of conventional photon beam therapy in pediatric patients with rhabdomyosarcomas.
3. To compare the dose distribution to tumor and surrounding normal structures using DVH's (Dose Volume Histograms) generated from the proton plan used to treat the patient and the photon plan generated for comparison purposes. Photon plans for comparison purposes will be completed for the first 79 patients.
4. To monitor the rates of event-free survival, overall survival and local control using proton radiotherapy.

## **III. SUBJECT SELECTION**

### **Inclusion criteria:**

1. Patients with biopsy proven newly diagnosed rhabdomyosarcoma.

2. Patients less than or equal to 30 years of age.
3. Patients must be treated with a standard accepted chemotherapy regimen for rhabdomyosarcoma (for example, according to IRS-IV, IRS-V, or future IRS study).
4. Patients may not have metastatic disease, unless aged 2-10 with embryonal histology.
5. Patients must be willing to receive follow-up care for a minimum of five years after treatment at the treating institution, including annual follow up visits. In the event that the patient is not from the local area and returning to the treating institution for follow up visits is too difficult, they must be willing to have their outside medical information (i.e. imaging studies, laboratory results and doctor or other health professional notes) released to the treating institution to track the results of treatment.
6. The patient or their legal guardian must give their informed consent.
7. Timing of radiation must be according to the IRS protocol upon which the patient is treated within either 35 days of last chemotherapy or surgery. (The clinical characteristics dictate the need for or/and timing of surgery and radiotherapy in relation to the chemotherapy.)

**Exclusion criteria:**

1. Patients with a life expectancy of less than 2 years.
2. Patients with co-morbidities that would make the use of radiation too toxic to deliver safely, such as serious local injury or collagen vascular disease.
3. Patients who are pregnant.
4. Patients who have previously received radiation therapy.

**Source of subjects and recruitment methods:**

Approximately 320 cases of pediatric rhabdomyosarcoma are diagnosed in the US per year[1]. Patients have been coming to MGH from all over the United States to be treated with proton irradiation and this trend is likely to continue. Patients will be recruited from MGH, BWH, Boston Children's Hospital, DFCI and MD Anderson Cancer Center. We estimate an annual accrual of 10 pediatric sarcoma patients across all participating sites, for a total accrual of 80 patients. Proton radiotherapy will be listed on the MGH Proton Center web site as a formal protocol and information of its availability will be made known to treating professionals through group (COG) meetings.

## **IV. SUBJECT ENROLLMENT**

### **Methods of enrollment: Registration Procedures**

#### **REGISTRATION PROCEDURES**

##### **General Guidelines for DF/HCC Institutions**

Institutions will register eligible participants in the Clinical Trials Management System (CTMS) OnCore. Registrations must occur prior to the initiation of protocol therapy. Any participant not registered to the protocol before protocol therapy begins will be considered ineligible and registration will be denied.

An investigator will confirm eligibility criteria and a member of the study team will complete the protocol-specific eligibility checklist.

Following registration, participants may begin protocol therapy. Issues that would cause treatment delays should be discussed with the Overall Principal Investigator (PI). If a participant does not receive protocol therapy following registration, the participant's registration on the study must be canceled. Registration cancellations must be made in OnCore as soon as possible.

### **Registration Process for DF/HCC Institutions**

DF/HCC Standard Operating Procedure for Human Subject Research Titled *Subject Protocol Registration* (SOP #: REGIST-101) must be followed.

### **General Guidelines for Other Investigative Sites**

Eligible participants will be entered on study centrally at the Coordinating Center by the Multi-center Coordinator. All sites should contact the Multi-center Coordinator to verify dose level availabilities prior to consent.

Following registration, participants should begin protocol therapy within 5 weeks. Issues that would cause treatment delays should be discussed with the Overall PI. If a participant does not receive protocol therapy following registration, the participant's registration on the study must be canceled. The Multi-center Coordinator should be notified of cancellations as soon as possible.

#### **Procedure for obtaining informed consent:**

The PI or Co-investigators will obtain informed consent from patient or the patient's parent or guardian after adequate explanation of the aims, methods, anticipated benefits and potential hazards of the study to the parent or guardian (and the patient if appropriate). If the patients, guardians and/or patient are non-English speaking, an interpreter will be made available to them and the enrolling site's IRB-approved process for obtaining informed consent from non-English speaking subjects will be followed. The patient or parent or guardian will be given a copy of the signed informed consent. The original signed informed consent will be retained per institutional policy.

#### **Treatment assignment:**

Treatment specifics such as dose and volume of radiation will be decided based on the national protocol, which is being followed for the patient's treatment and/or the clinical situation including histology and tumor site.

### **Study Visits and Measured Parameters**

#### **Baseline staging requirements:**

1. Complete history and physical by a radiation oncologist, medical oncologist or surgeon.
2. Other baseline laboratories or evaluations necessary to evaluate function of organs that the tumor effects or that the treatment is likely to effect. For example, if the thyroid gland will be irradiated or compromised by tumor a TSH and thyroid function tests are indicated for a baseline test. Likewise, if the tumor is located in the orbit, full vision testing to the extent that it is possible should be achieved prior to irradiation. (Please refer to Studies at Baseline section for additional details).
3. CT or MRI scan (preferably with contrast or gadolinium if not contraindicated in the patient) of the original tumor or tumor site at the time of diagnosis.
4. CT scan of the chest to rule out lung metastases at time of diagnosis
5. Bone marrow biopsy to rule out bone marrow involvement at time of diagnosis for patients with intermediate or high-risk disease (in general, alveolar histology, unfavorable sites with gross residual disease and/or metastatic disease). Refer to the COG protocol breakdown of risk if there is a question. Bone marrow biopsy is not required for low-risk patients.
6. PET or bone scan at time of diagnosis.
7. Pathology review at treating institution.

**Schedule of Assessments:**

Data Set	Completed prior to enrollment or within 35 days after enrollment	Weekly Visit During RT	At least 1 visit after RT within 3 months (suggested = 6 weeks after RT)	Yearly Follow-Up (+/- 6 months)
Age	x			x
Sex	x			
Hx and P	x	x	x	x
Acute Toxicity Assessment		x	x	

Bone Marrow Biopsy at diagnosis for intermediate and high-risk patients	x			
PET or Bone scan	x			
Chest CT at diagnosis	x			
CT or MRI of the original site of disease (plain film if it is an extremity), at diagnosis	x			x (per IRS guidelines)
Brain MRI or CT if parameningeal, at diagnosis	x			
Late Toxicity Assessment				x
Site related tests that will be repeated at yearly f/u (see below).	x			x

**Note:** Many patients have received surgery and chemotherapy prior to being referred for radiation therapy. The timing of the radiation therapy is dictated by the treatment protocol or by best clinical judgment. Some patients who are very young at diagnosis (such as <1 year old) are treated off-protocol and given the full 48 weeks of chemotherapy prior to their radiation therapy in order to allow maximal growth and development before radiation therapy.

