**Acute Toxicity:**

Acute toxicity will be scored at weekly status check visits by the radiation oncology nurse or doctor. In addition, acute toxicity will be scored at least one time within the 3 months following completion of radiation therapy. This may be scored by the local pediatric oncologist if the patient does not return to the treating institution for a follow-up visit during this time frame. The recommended evaluation time for acute toxicity after radiotherapy is 6 weeks following completion, but may be at any time during the 3 months after treatment. In addition, any event requiring admission must be recorded. Acute toxicities will be graded according to the Common Terminology Criteria for Adverse Events (CTCAE), Version 3.0.

All toxicities and adverse events that are possibly, probably or definitely related to radiation therapy will be captured on the case report forms.

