## **VI. BIOSTATISTICAL ANALYSIS**

Primary outcomes are acute and late complications following proton beam irradiation to the tumor or tumor bed. Late complications are defined as the delayed effects attributable to radiation which occur > 90 days following completion of radiation, while acute side effects are those occurring during radiotherapy or up to 90 days after the last dose. Allowing for 5% inflation for unevaluable patients due to ineligibility or early dropout, the revised accrual goal is a total of 115 patients with a minimum follow-up of another 2

years following the patient enrollment for observing the late complications of proton beam irradiation.

The goal of utilizing protons is an improvement in the historical complication rate, which varies by site and type of complication. The literature for parameningeal or other head and neck rhabdomyosarcomas has reported endocrine effects occurring in 50-100% and impaired orbital function in 70-100% of patients (23-27). For children treated for pelvic tumors, late effects were significantly higher among patients treated, ranging from 54% to 77% (28). Across all anatomic sites, the likelihood of one or more reported late effects has been approximately 70% or more among those who received conventional radiation. Among a total of 110 patients, the probability is 81% that 70 or fewer of them will develop any late effect if the overall complication rate is truly decreased to 60% with the use of protons. The decision rule is associated with only 9% probability if the underlying rate were truly similar to the 70% historical rate observed with conventional radiation.

Due to a difference in the radiation doses used for treating patients with different tumor characteristics (typical doses are 36 Gy, 41.4 Gy, 45 Gy and 50.4 Gy), the outcomes will be analyzed according to dose group,  $\leq$  45 Gy and  $\geq$  45 Gy. Data on the enrolled patients shows a 1:4 ratio in the distribution of patients receiving low versus intermediate radiation doses. Constitutional symptoms, namely fatigue and malaise, as well as skin reactions in the radiation port will be analyzed according to dose group.

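### No toxicity grade is recorded before the first radiation fraction, so effects of earlier surgery, chemotherapy or tumour may be counted as radiation toxicity, chiefly in the acute endpoint

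*Combined protocol and SAP*

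**What the plan says.** Three rows of the Schedule of Assessments in section IV matter.

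- "Acute Toxicity Assessment" is marked at the weekly visits during radiation and at the visit within 3 months after it.
- "Late Toxicity Assessment" is marked at yearly follow-up only.
- "Site related tests that will be repeated at yearly f/u (see below" is marked in the first column and again yearly.

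The first column covers completion before enrollment or within 35 days after it. The note under the table says "Many patients have received surgery and chemotherapy prior to being referred for radiation therapy", and adds that some children under 1 year receive the full 48 weeks of chemotherapy first.

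The Acute Toxicity subsection repeats the timing: "Acute toxicity will be scored at weekly status check visits by the radiation oncology nurse or doctor", with at least one further scoring in the 3 months after treatment. Case report forms capture any event judged at least possibly related to radiation.

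Baseline staging requires "Complete history and physical by a radiation oncologist, medical oncologist or surgeon", and evaluations of organs affected by the tumour or likely to be affected by treatment. Studies at Baseline adds weight and height, and site-specific tests.

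Section VI makes acute and late complications the primary outcomes. Late complications must be attributable to radiation and occur more than 90 days after it ends. Acute effects are defined only by falling between the start of radiotherapy and 90 days after the last dose. Section VI also plans that "Constitutional symptoms, namely fatigue and malaise, as well as skin reactions in the radiation port will be analyzed according to dose group".

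**The concern.** The second aim is "To assess acute side effects from irradiation using proton beam therapy in place of conventional photon beam therapy in pediatric patients with rhabdomyosarcomas", and the first aim asks the same of late complications. Both concern what irradiation causes. A child who arrives tired, underweight, with low counts or with a cranial-nerve deficit after induction treatment has that state graded for the first time during radiation. The assessor then decides whether it is possibly related to radiation, with no earlier grade to compare. Nothing in the text reviewed says that a toxicity must be new or worse than before radiation.

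At stake are the acute toxicity rates, the tissue-specific estimates and the comparison of constitutional symptoms between dose groups. For late effects, a count under the 70-of-110 rule could also include deficits that pre-date radiation.

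**Working it through.** **1. Can an effect present before radiation enter the endpoint?**

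| Endpoint | Definition in section VI | Filter at data capture | Pre-radiation reference |
|---|---|---|---|
| Acute | Timing only | At least possibly related | No graded form; ungraded history and physical, weight and height |
| Late | Timing and attribution to radiation | At least possibly related | No graded form; as above, plus organ-function evaluations and site tests |

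For acute effects the only barrier is a low relatedness threshold. Late effects have the attribution wording and more baseline data.

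**2. Is the first column a pre-radiation column?** Not necessarily. It allows 35 days after enrollment. Section IV lets DF/HCC participants start therapy once registered, and asks other sites to start within 5 weeks, which is also 35 days. A baseline item can therefore follow the first fraction. Site tests have their own windows: audiometry up to 10 weeks after radiation starts, and eye and neuro-psychiatric evaluations within 6 months either side. Endocrine and dental evaluations are recommended, not required. No listed test addresses fatigue, malaise or skin.

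**3. Dose groups.** Treatment Assignment and Dose Specification tie dose to histology, setting, tumour site and the national protocol. These may plausibly also govern earlier chemotherapy, but the documents do not show it. Section VI reports a 1:4 split between low and intermediate dose. If that held among 110 patients, the groups would be 110 × 1/5 = 22 and 110 × 4/5 = 88. One carried-over case would then move the low-dose rate by 1/22 = 4.5 points and the other by 1/88 = 1.1 points.

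**4. The plan's late-effect rule.** With X binomial (n = 110, rate p), success is X ≤ 70.

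- P(X ≤ 70) at p = 0.60 is 0.809 (plan: 81%).
- P(X ≤ 70) at p = 0.70 is 0.090 (plan: 9%).

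Both figures reproduce.

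**5. Sensitivity to carry-over.** The amounts below are assumptions; the documents give none.

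(a) A fixed share of all patients is added to a true 60%:

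- 3 points: p = 0.63, P = 0.590.
- 5 points: p = 0.65, P = 0.417.

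(b) A share q of patients without a true radiation effect is miscounted, so the observed rate is 0.60 + 0.40q:

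| q | Observed rate | P(X ≤ 70) |
|---|---|---|
| 5% | 0.62 | 0.672 |
| 10% | 0.64 | 0.504 |
| 15% | 0.66 | 0.333 |
| 20% | 0.68 | 0.189 |
| 25% | 0.70 | 0.090 |

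The two scales differ: 5 points of all patients is q = 0.05/0.40 = 12.5%.

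**6. The opposite error.** Suppose the historical 70% contains 5 points of pre-existing deficits, and the trial counted only new or worsened effects. A proton rate equal to history would then be observed as 0.70 − 0.05 = 0.65, and the chance of declaring success would rise from 0.090 to 0.417.

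**The case against.** A reader might infer that pre-existing effects definitely are scored as radiation toxicity. The documents do not support that. Late complications must be attributable to radiation, captured events must be at least possibly related to it, and a deficit documented beforehand should fail a careful attribution. That part of the objection stands: such effects may be counted, not must be.

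A reader might also infer that baseline status goes unrecorded outside a few head and neck tests. That too goes beyond the text. The organ-function requirement is general, with thyroid and vision given as examples. Weight and height are recorded for everyone, and a cranial-nerve deficit should appear in a physical examination. What remains missing is a grade, a date that is certain to precede radiation, and a rule for using either.

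The third tempting reading is that power for the late rule truly falls from 81% to 42%. That figure rests on an assumed 5 points and leaves the 70% benchmark untouched. The benchmark is a rate of reported late effects after conventional radiation, in a disease treated with combined modalities, and may contain the same carry-over. If so, part or all of the bias cancels in that comparison. The cancellation would not help the acute rates, the tissue-specific estimates or the dose-group comparison.

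Two further limits stand. A single pre-radiation grade cannot separate chemotherapy toxicity that arises during radiation, a confounder section VI already acknowledges. Appendices I to III appear in the contents but were not in the text reviewed, so a baseline rule there cannot be excluded.

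**Conclusion.** The concern holds in a limited form. The schedule contains no graded toxicity assessment before the first fraction, and the text reviewed gives no rule for change from a pre-radiation state, although many patients arrive already treated. The weakness is clearest for acute toxicity and for fatigue and malaise by dose group. It is smaller for late effects, which have partial protection.

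The size of the bias cannot be derived from the documents. The late rule is sensitive to modest misclassification (81% falling to between 67% and 50% for an assumed q of 5% to 10%), but this shows sensitivity and is not an estimate. The net direction against the 70% historical rate is uncertain. The change is worth making because it is cheap and serves two primary outcomes.

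**What to change.** 1. In the Schedule of Assessments, add a graded toxicity assessment explicitly dated before the first fraction, completed at a history and physical done before radiation starts. A mark in the existing first column would not be enough, because that column runs to 35 days after enrollment.
2. For patients already treated, abstract the grade from pre-radiation records where these exist, and report how many could not be graded.
3. In section VI, report acute toxicities, including fatigue, malaise and skin reactions by dose group, as new or worsened from the pre-radiation grade.
4. For late effects, keep the 70-of-110 rule on the plan's existing definition and report the new-or-worsened count beside it. Replace the count in the rule only if the historical 70% can be shown to have been counted the same way; otherwise the change could favour success.
5. If an appendix already holds a baseline scoring rule, refer to it in section IV.

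The cost is one extra form at an existing visit, some retrospective abstraction with incomplete records, and lower reported acute toxicity counts. No visit, procedure or treatment changes.
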